4.7.3 Additional safety assessments

4.7.3.1 **Laboratory variables, vital signs and electrocardiograms (ECGs)**

The following laboratory variables, vital signs and electrocardiogram (ECG) variables will be analyzed. They will be converted into standard international units.

- Hematology:
 - Red blood cells and platelets and coagulation: hemoglobin, hematocrit, red blood cell count, platelet count
 - White blood cells: white blood cell count, neutrophils, lymphocytes, monocytes, basophils, eosinophils
- Clinical chemistry:
 - **Metabolism:** glucose, total cholesterol, total protein, creatine phosphokinase,
 - **Electrolytes:** sodium, potassium, chloride, calcium, bicarbonate,
 - **Renal function:** creatinine, blood urea nitrogen, uric acid,
 - **Liver function:** alanine aminotransferase, aspartate aminotransferase, alkaline phosphatase, lactate dehydrogenase, total bilirubin, albumin,
 - **Pregnancy test:** Serum β -human chorionic gonadotropin (all female participants) will be performed at screening (V1) in women of childbearing potential, and a urine pregnancy test will be performed at V2 and every 4 weeks thereafter,
 - **Hepatitis screen:** hepatitis B surface antigen (HBs Ag), hepatitis B surface antibody (HBs Ab), hepatitis B core antibody (HBc Ab), hepatitis C virus antibodies (HCV Ab) will be tested at screening (V1). In case of results showing HBs Ag (negative) and HBc Ab (positive), an hepatitis B virus (HBV) deoxyribonucleic acid (DNA) testing will be performed and should be confirmed negative prior to randomization. In case of results showing HCV Ab (positive), an HCV ribonucleic acid (RNA) testing will be performed and should be confirmed negative prior to randomization,
 - **HIV screen:** Anti-HIV-1 and HIV-2 antibodies will be tested at Visit 1,

- Urinalysis:
 - **Urinalysis** will include specific gravity, pH, glucose, ketones, blood, protein, nitrate, leukocyte esterase, urobilinogen and bilirubin. In case the urine dipstick test result is abnormal, a urine sample should be sent into the central laboratory for microscopic and macroscopic examination.
- Vital signs: pulse rate (beats per minute), systolic and diastolic blood pressure (mmHg) in a semi-supine or sitting position after 5 minutes, weight, respiratory rate (breaths per minute), temperature (degrees Celsius) and height (screening only),
- ECG variables: heart rate, PR, QRS, QT, and QTc intervals after 10 minutes of rest in the supine position.

Data below the lower limit of quantitation/detection limit (LLOQ) will be replaced by half of the LLOQ, data above the upper limit of quantification will be replaced by ULOQ value.

Quantitative analyses

For all laboratory variables and vital signs variables above, descriptive statistics for results and changes from baseline will be provided for each analysis window, the last value and the worst value during the on-treatment period. These analyses will be performed using central measurements only (when available) for laboratory variables.

For all parameters, mean changes from baseline with the corresponding standard error will be plotted over time.

Analyses according to PCSA

Potentially clinically significant abnormality (PCSA) analyses will be performed based on the PCSA list currently in effect at Sanofi at the time of the database lock. For parameters for which no PCSA criteria are defined, similar analyses will be done using the normal range, if applicable.

Analyses according to PCSA will be performed based on the worst value during the treatment-emergent period, using all measurements (either local or central, either scheduled, nonscheduled or repeated).

For laboratory variables, vital signs and ECG variables above, the incidence of participants with at least one PCSA during the treatment-emergent period will be summarized regardless of the baseline level and according to the following baseline status categories:

- Normal/missing
- Abnormal according to PCSA criterion or criteria

Additional analyses for suspect drug-induced liver injury

The following additional analyses will be performed for drug-induced liver injury:

- Time to onset of the initial ALT or aspartate aminotransferase (AST) elevation ($>3 \times \text{ULN}$) and total bilirubin elevation ($>2 \times \text{ULN}$) during the treatment-emergent period will be analyzed using Kaplan-Meier method.

- A graph of the distribution of peak values of ALT versus peak values of total bilirubin during the treatment-emergent period will be provided.
- For each liver function test (eg, ALT), participants having a PCSA (eg, ALT >5 ULN) will be summarized using the following categories: Returned to baseline PCSA status (or returned to value \leq ULN in case of missing baseline) before last IMP dose, Returned to baseline PCSA status after last IMP dose, Never returned to baseline PCSA status, No assessment after elevation. This summary will be performed by categories of elevation (ALT >3, >5, >10, >20 ULN).

4.8 OTHER ANALYSES

4.8.1 PK analyses

Predose serum dupilumab concentrations at Visit 2 (Day 1), dupilumab trough levels at Week 12, Week 24/EOT and posttreatment serum dupilumab at Week 36 will be provided.

Serum concentrations of SAR231893 (REGN668) will be summarized in the PK population using arithmetic and geometric means, SD, standard error of the mean (SEM), coefficient of variation (CV), minimum, median and maximum per sampling time. If date and/or time of the drug injection and/or sampling is missing then the concentration will not be taken into account. For drug-treated participants, where concentration values are below the lower limit of quantification (LLOQ), one-half of the LLOQ will be used. Values will be expressed in the tables with no more than three significant figures. For participants in the placebo group, concentration values are below the LLOQ will be taken into account with a plasma concentration considered equal to 0.

4.8.2 Immunogenicity analyses

Dupilumab anti-drug antibody (ADA) status (negative or titer value, if positive in the ADA assay) at Visit 2 (Day 1), Week 12, Week 24/EOT and follow up at Week 36 will be provided. The neutralizing antibody status for ADA positive samples will be provided.

Incidence will be provided for the following ADA response categories:

Pre-existing immunoreactivity is defined as:

An ADA positive response in the assay at baseline with all post first dose ADA results negative, OR an ADA positive response at baseline with all post first dose ADA responses less than 4-fold over baseline titer levels.

Treatment-emergent ADA responses are defined as:

A positive response in the ADA assay post first dose, when baseline results are negative or missing.

Treatment-emergent ADA responses are further classified as Persistent, Indeterminate or Transient

- a) Persistent Response- defined as a treatment-emergent ADA response with two or more consecutive ADA positive sampling time points, separated by greater than ($>$) 12-week period (84 days), with no ADA negative samples in between.
- b) Indeterminate Response- defined as a treatment-emergent response with only the last collected sample positive in the ADA assay.
- c) Transient Response - defined as a treatment-emergent response that is not considered persistent OR indeterminate.

Treatment-boosted response is defined as:

An ADA positive response in the assay post first dose that is greater-than or equal to 4-fold over baseline titer levels, when baseline results are positive.

Titer values (Titer value category)

- Low (Titer <1000)
- Moderate ($1,000 \leq \text{Titer} \leq 10,000$)
- High (Titer $>10,000$)

The following summary will be provided based on ADA population:

- Number (%) of participants with pre-existing immunoreactivity
- Number (%) of participants with treatment-emergent ADA
- The summary statistics (including number, median, Q1, Q3, minimum and maximum) of the peak post-baseline titer for participants with treatment-emergent ADA, and participants with persistent, indeterminate and transient ADA response
- Number (%) of participant with transient treatment-emergent ADA
- Number (%) of participants with persistent treatment-emergent ADA
- Number (%) of participants with indeterminate treatment-emergent ADA
- Number (%) of participants with treatment-boosted ADA
- The summary statistics (including number, median, Q1, Q3, minimum and maximum) of the peak post-baseline titer for participants with treatment-boosted ADA
- The summary statistics (including number, mean, SD, median, Q1, Q3, minimum and maximum) of the ratio of peak post-baseline titer to baseline titer for participants with treatment-boosted ADA
- Listing of ADA peak titer levels and neutralizing antibody status
- Number (%) of participants with neutralizing antibody status

Kinetics of treatment-emergent ADA response

Number (%) of participants with treatment-emergent ADA positive response at each visit will be summarized by each intervention group.

Plot of percentage of participants with treatment-emergent ADA positive response at each visit will be provided by each intervention group.

4.8.2.1 Association of Immunogenicity with Exposure, Safety and Efficacy

The safety and efficacy analysis mentioned below will be conducted using the following categories:

ADA positive participants: Participants with treatment-emergent or treatment-boosted response.

ADA negative participants: Participants with pre-existing immunoreactivity or negative in the ADA assay at all time points.

Impact of ADA on PK profile

Potential associations between ADA variables (eg, ADA peak titers, neutralizing antibody status, treatment-emergent, persistent, indeterminate and transient response, treatment-boosted) and impact on serum concentration profile of dupilumab may be explored. Plot of serum concentration of functional dupilumab versus visit will be provided by ADA variables for each dupilumab dose group. Individual participant plots of dupilumab concentration according to ADA status will be provided.

Impact of ADA on clinical efficacy endpoints

Associations between the ADA variables (eg, ADA peak titers, neutralizing antibody status, treatment-emergent, persistent, treatment-boosted) and the primary efficacy endpoint may be explored for the dupilumab dosed group.

Association of ADA with clinical safety endpoints

Association of safety versus ADA status may be analyzed in the ADA population. The safety assessment may focus on the following events:

- Severe injection site reactions last longer than 24 hours or serious injection site reactions
- Hypersensitivity reactions (SMQ (20000214) hypersensitivity narrow search confirmed by medical review)
- Anaphylactic reactions (SMQ (20000021) anaphylactic reaction narrow search)

Associations between ADA variables (eg, ADA peak titers, neutralizing antibody status, treatment-emergent, persistent and treatment-boosted) and safety may be explored.

4.8.3 Pharmacodynamic/genomics endpoints

Venous blood samples will be collected at Visit 2 (Week 0), Visit 3 (Week 12), Visit 4 (Week 24/EOT), and Visit 5 (Week 36), for measurement of total serum IgE. Total IgE will be measured using validated quantitative methods.

For those participants (with exception of adolescent and children) who consent to the optional pharmacogenetic/pharmacogenomic sample collection section of the ICF, serum/plasma for archival samples for possible future analysis of potential biomarkers of drug response, disease activity, safety, and the Type 2 inflammation pathway, and blood samples for exploratory genetic

analysis of DNA or RNA will be collected and stored for possible future use. Participation is optional. Participants who do not wish to participate in the genetic research may still participate in the study.

For those participants (with exception of adolescent and children) who consent to the optional basophil activation (substudy), samples will be taken at Visit 2, Visit 3 (Week 12) and Visit 4 (Week 24/EOT).

For those participants (with exception of adolescent and children) who consent to the optional skin biopsy (substudy), the sample will be taken from lesion and non-lesion skin using punch biopsy at Visit 2 and Visit 4 (Week 24/EOT).

Total IgE will be summarized in the safety population defined as participants who actually received at least 1 dose or part of a dose of the IMP. Baseline values will be the last value collected prior to the first IMP. Descriptive statistics (including number, mean, SD, median, Q1, Q3, min, max) of biomarkers at baseline will be summarized.

Summary plots (median+/- standard error of the mean) on values at each visit, absolute changes from baseline and percent changes from baseline will be provided for the total IgE by intervention group and visit.

Exploratory analysis of DNA/RNA will be addressed in a separate document.

The analyses of the basophil activation and skin biopsy substudy will be addressed in a separate document.

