of IL-4/IL-13 by dupilumab represents a novel therapeutic approach for CSU patients. In a small case series of patients who had concurrent AD and CSU and were resistant to omalizumab, treatment with dupilumab improved their urticaria. This further supports the rationale to target aberrant IL-4/IL-13 signaling with dupilumab in patients with CSU. As this is a novel therapy that acts further upstream than IgE-targeted therapies, the clinical trials proposed here will test the efficacy of dupilumab in patients who have failed anti-histamines alone or who have failed both anti-histamines and omalizumab. Efficacy in patients who were intolerant to omalizumab will also be assessed. The master protocol EFC16461 will include 3 studies in CSU patients who remain symptomatic despite the use of H1-AH treatment - 2 studies will be in patients who are omalizumab naïve (Study A and Study C) and the third study in patients who are intolerant or incomplete responders to omalizumab (Study B). The selected dosing regimen is dupilumab 300 mg every 2 weeks (q2w) with a loading dose of 600 mg for adults; 300 mg q2w with a loading dose of 600 mg for adolescents  $\geq$ 60 kg at screening OR 200 mg q2w with a loading dose of 400 mg for adolescents <60 kg at screening; and 200 mg q2w with a loading dose of 400 mg for children  $\geq$ 6 to <12 years of age with weight  $\geq$ 30 kg at screening OR 300 mg q4w with a loading dose of 600 mg for children  $\geq$ 6 to <12 years of age with weight <30 kg and  $\geq$ 15 kg at screening. This dose is expected to achieve concentrations in serum that saturate the IL-4/IL-13 receptor and hence it is expected to provide the maximum benefit and therefore to achieve the optimal benefit/risk ratio in this patient population.

LIBERTY-CSU CUPID Study A was completed and demonstrated that dupilumab at the above-mentioned dosing regimen is efficacious versus placebo in participants with CSU who remain symptomatic despite the use of H1 antihistamine (H1-AH) treatment (6). The trial included a total of 138 participants (132 adults, 4 adolescents and 2 children), with 68 participants in the placebo group and 70 participants in the dupilumab group.

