4.8.3 Pharmacodynamic/genomics endpoints

Venous blood samples will be collected at Visit 2 (Week 0), Visit 3 (Week 12), Visit 4 (Week 24/EOT), and Visit 5 (Week 36), for measurement of total IgE in serum. Total IgE will be measured using validated quantitative methods.

For those participants (with exception of adolescents) who consent to the optional pharmacogenetic/pharmacogenomic sample collection section of the ICF, serum/plasma for archival samples for possible future analysis of potential biomarkers of drug response, disease activity, safety, and the Type 2 inflammation pathway, and blood samples for exploratory genetic analysis of DNA or RNA will be collected and stored for possible future use. Participation is optional. Participants who do not wish to participate in the genetic research may still participate in the study.

For those participants (with exception of adolescent) who consent to the optional basophil activation (substudy), samples will be taken at Visit 2, Visit 3 (Week 12) and Visit 4 (Week 24/EOT).

For those participants (with exception of adolescent) who consent to the optional skin biopsy (substudy), the sample will be taken from lesion and non-lesion skin using punch biopsy at Visit 2 and Visit 4 (Week 24/EOT).

Total IgE will be summarized in the safety population defined as participants who actually received at least 1 dose or part of a dose of the IMP. Baseline values will be the last value collected prior to the first IMP. Descriptive statistics (including number, mean, SD, median, Q1, Q3, min, max) of biomarkers at baseline will be summarized.

Summary plots (median +/- interquartile range) on values at each visit, absolute changes from baseline and percent changes from baseline will be provided for the total IgE by intervention group and visit.

Exploratory analysis of DNA/RNA will be addressed in a separate document.

The analyses of the basophil activation and skin biopsy substudy will be addressed in a separate document.

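### Study A total IgE plots pair the median with the standard error of the mean, a bar that describes neither the precision of the median nor the spread around it

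*SAP*

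**What the plan says.** The Study A SAP, section 4.8.3, plans "Summary plots (median+/- standard error of the mean) on values at each visit", and applies the same format to absolute and percent changes from baseline in total IgE, by intervention group and visit.

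The same-numbered section of the Study B SAP, and again of the Study C SAP, plans "Summary plots (median +/- interquartile range) on values at each visit, absolute changes from baseline and percent changes from baseline". The three sentences otherwise match closely. No SAP explains the difference, and the change table in the Study B SAP does not list it.

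Two other places in the Study A SAP bear on the point:

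- Section 4.8.3 also states "Descriptive statistics (including number, mean, SD, median, Q1, Q3, min, max) of biomarkers at baseline will be summarized". Quartiles are therefore planned, but only at baseline.
- Section 4.7.3.1 (laboratory and vital-sign plots) pairs statistics consistently: "mean changes from baseline with the corresponding standard error will be plotted over time".

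**The concern.** A bar around a plotted point is read in one of two ways: as the precision of that point, or as the spread of the data around it. The SEM is neither for a median. It is the sample SD divided by the square root of n, so it measures how precisely the mean is known. When the mean and median differ, as they do in skewed data, a few large values can drive it.

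Comparability across studies is also at stake. Total IgE is the only pharmacodynamic parameter in the protocol (sections 8.6 and 8.8), and Study C was added to stand beside Study A. SEM bars shrink as n grows and quartile bars do not, so the Study A and Study C plots could look very different even if the underlying IgE data were alike.

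**Working it through.** **Step 1: the mismatch.** This needs no distributional assumption. The plotted statistic is the median and the bar is SD/√n, which is an estimate of the standard error of the mean. Nothing in its construction makes median ± SEM an interval for the median. Section 4.7.3.1 of the same SAP pairs the mean with its own standard error. Section 4.8.3 of the Study B and C SAPs pairs the median with a quartile-based statistic. The Study A IgE plot does neither.

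**Step 2: how far the SEM can be from the standard error of the median.** The plan states no figure to reproduce, and the documents give no IgE mean, SD or shape. The inputs are:

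- n = 70, from the Study A arm sizes in Protocol section 2.1 ("with 68 participants in the placebo group and 70 participants in the dupilumab group"). These are randomized counts; the number with IgE data at a visit may be lower.
- Log-normal IgE with median M = 100 (assumption, used only for scale).
- Log-scale SD s = 1.0, 1.25 and 1.5 (assumption, shown as a range).

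Formulas:

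- Population SEM = M·exp(s²/2)·√(exp(s²) − 1)/√n. At s = 1.5: 100 × 3.080 × 2.913/8.367 = 107.
- Approximate SE of the median = √(π/2)·s·M/√n. At s = 1.5: 1.2533 × 1.5 × 100/8.367 = 22.5.

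Under strong skew the sample SEM is usually well below its population value. Because a plot uses the sample SEM, it was simulated (40,000 samples per row). The typical SEM below is the median across samples.

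| log-SD | population SEM | typical sample SEM | simulated SE of median | ratio, typical SEM to SE of median | samples with median − SEM below 0 |
|---|---|---|---|---|---|
| 1.0 | 26 | 22 | 15 | 1.5 | 0.1% |
| 1.25 | 51 | 38 | 19 | 2.0 | 3% |
| 1.5 | 107 | 64 | 23 | 2.8 | 22% |

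Across this range the SEM overstates the uncertainty of the median by a factor of about 1.5 to 2.8. At n = 68 the results are almost the same.

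**Step 3: the replacement bar.** Log-normal quartiles are M·exp(±0.6745s): 51 and 196 at s = 1.0, 43 and 232 at 1.25, 36 and 275 at 1.5. Bars drawn from Q1 to Q3 stay positive for visit values. The Study B and C wording, "Summary plots (median +/- interquartile range) on values at each visit", can also be read as the median plus and minus the width Q3 − Q1. The lower limits would then be:

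- s = 1.0: 100 − (196 − 51) = −45
- s = 1.25: 100 − (232 − 43) = −89
- s = 1.5: 100 − (275 − 36) = −139

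In simulation this lower limit is negative in about 97% of samples at s = 1.0 and over 99% at 1.25 and 1.5.

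**The case against.** The case for leaving this alone has four parts.

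- **Study A is finished.** Its SAP version 2 is dated 16 June 2021, and Protocol amendment 05 (March 2022) reports its results. The Study B SAP (7 December 2021) and the Study C SAP already use the interquartile range. This stands as a limit on importance: the action falls on re-issued or integrated outputs. It does not make the specified bar correct.
- **The plot is descriptive.** IgE is not in the testing hierarchy, and no decision rule uses it. This stands.
- **Harm to comparability is conditional.** No integrated IgE display is specified; the protocol only allows that integrated analyses may be done. This stands in part, since the separate Study A and Study C plots would still be set side by side.
- **The SEM is a defined statistic and the plan names it.** This is true, so the bars are not meaningless. They describe a quantity other than the one plotted.

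A reader might also infer that the Study A bars would reach impossible negative IgE values. The documents do not support that as an expectation. It needs strong assumed skew, and even at log-SD 1.5 it occurs in only about 22% of simulated samples; the typical lower limit there is about +34. For the absolute and percent changes, values below zero are legitimate.

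**Conclusion.** The Study A specification is wrong as written: the bar does not belong to the plotted statistic, and it differs in kind from the bar in Studies B and C. That conclusion rests on the text and on the definition of the SEM alone.

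The size rests on assumptions. For log-normal IgE at n = 70 and median 100, the typical SEM is 22, 38 and 64 against a standard error of the median of 15, 19 and 23 at log-SD 1.0, 1.25 and 1.5. With little skew the gap would be smaller.

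Two further inferences go beyond the documents. The Study B and C wording is not a ready-made model, because its literal reading gives a worse lower limit than the SEM does. Nor are the needed quartiles already planned throughout, because Study A section 4.8.3 lists them at baseline only.

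The importance is low. No hypothesis test, type I error or efficacy conclusion is affected.

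**What to change.** In any remaining or re-issued Study A output, and in any integrated display, plot median total IgE with bars drawn from Q1 to Q3 and say so in the figure legend. Use the same format for the absolute and percent changes. Produce Q1 and Q3 at Weeks 12, 24 and 36 and for both change measures, in addition to baseline.

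In section 4.8.3 of the Study B and C SAPs, replace the plus-or-minus phrasing with: median with Q1 to Q3.

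The cost is re-running one descriptive plot for a completed study, routine quartiles at the post-baseline visits, and a one-line wording change in each of the other two SAPs.
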